13.1.2 Sensitivity Analyses

A completer analysis will be performed. That is the primary analysis will be repeated for subjects who complete Month 6 visit, i.e. analysis based on the observed data. Any data collected at and after rescue visits will not be used. The primary analysis will also be repeated based on per protocol set.

13.2 Secondary Efficacy Endpoints

Change from baseline in BCVA and CCT at Month 6 will be analyzed using Analysis of covariance (ANCOVA) for the full analysis set. The model will include treatment arm as a categorical variable and baseline as a covariate. Treatment comparison of BCVA and CCT at Month 6 will be conducted. Point estimates, 95% confidence intervals and p-values will be provided. Any data collected at and after rescue visits will not be used. As stated in Section 7.10, LOCF will be used to impute the missing values.

Proportion of subjects having ≥ 10 -letter improvement (2-line gain) from baseline in BCVA at Month 6 will be analyzed using the same method as the analyses of the primary endpoint. For this analysis, missing data will be imputed using the same method as the primary endpoint.

Descriptive summary statistics will be provided for all the secondary endpoints listed in Section 4.2.1.2. Any data collected at and after rescue visits will not be used.

In addition, 3, 2, and 1-line gain and 3, 2, and 1-line loss in BCVA will be summarized by dose and visit. Change from baseline within 10 letters (<10 letters gain and <10 letters loss) will be labeled as 0-line and will also be part of the summary. Summaries will include count, percentage and cumulative percentages. Any data collected at and after rescue visits will not be used.

Change from baseline in BCVA and CCT will also be summarized descriptively using LOCF imputation. Any data collected at and after rescue visits will not be used.

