Statistical Methods	
Analysis Sets The Full Analysis Set (FAS) will be defined as all eligible subjects who received any amount of study drug during intracameral injection. All subjects in FAS will be analyzed according to the treatment they actually received. Per Protocol Set (PPS) is a subset of FAS who completed the study without major protocol deviations. The Safety Analysis Set will be the same as FAS.
 
Efficacy Analyses For the primary endpoint and other binary endpoints, number and percentage of subjects, with associated 2-sided exact (Clopper-Pearson) 95% confidence intervals (CIs), will be presented by treatment in each category (response, non-response). The distribution of responders will be compared between treatment arms using a two-sided Fisher's exact test.
 
Analyses of change from baseline in BCVA, CCT and [REDACTED] will be conducted using the Full Analysis Set and a restricted maximum likelihood based mixed-effect model for repeated measures to evaluate the effect over time. The dependent variable will be the change from baseline. The model will include treatment arm (3 levels), categorical time, treatment arm by time interaction, and baseline value as a covariate.
 
Safety Analyses All safety analyses will be conducted on the Safety Analysis Set. No formal statistical tests of treatment difference are planned.
 
AEs will be coded using the Medical Dictionary for Regulatory Activities (i.e., AEs that begin or worsen in severity after initiation of study drug) will be summarized by treatment arm and overall in the study eye. Non-ocular TEAEs will also be summarized. Additionally, TEAEs and serious AEs will be summarized in a similar manner by maximum severity and relationship to study drug and the surgical procedure.
 
Changes from baseline of quantitative measurements (ophthalmic evaluations, laboratory findings) will be summarized by treatment arm and timepoint.

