10.7 Efficacy Analyses

For the primary endpoint and other binary endpoints, number and percentage of subjects, with associated 2-sided exact (Clopper-Pearson) 95% confidence intervals (CIs), will be presented by treatment in each category (response, non-response). The distribution of responders will be compared between treatment arms using a two-sided Fisher's exact test.

Analyses of change from baseline in BCVA, CCT and [REDACTED] will be conducted using the full analysis set and a restricted maximum likelihood based mixed-effect model for repeated measures to evaluate the effect over time. The dependent variable will be the change from baseline. The model will include treatment arm, categorical time, treatment arm by time interaction, and baseline value as a covariate.

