7.7 Adjustments for Multiplicity

7.8 Adjustment for Covariates

Change from baseline in BCVA and CCT at Month 6 will be analyzed using Analysis of covariance (ANCOVA) for the full analysis set. Baseline of BCVA and CCT will be used as covariate for the adjustment.

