7.10 Missing Data Imputation for Efficacy Endpoints

The study primary endpoint is proportion of subjects having a ≥ 15 -letter improvement (3-line gain) from baseline in best-corrected visual acuity (BCVA) at Month 6. For the primary analysis, intercurrent events will be addressed using composite variable strategies. That is subjects who received any rescue surgeries prior to Month 6 or drop out the study due to any reasons prior to Month 6 will be imputed as treatment failure (i.e. not improve by ≥ 15 letters).

For the statistical analysis, the following two binary endpoints will be imputed using the same method as the primary endpoint:

- proportion of subjects having a ≥ 10 -letter improvement (2-line gain) from baseline in best-corrected visual acuity (BCVA) at Month 6
-

In addition, the following two continuous endpoints will be imputed using last observation carried forward (LOCF) for their statistical analyses:

- best-corrected visual acuity (BCVA)
- central corneal thickness (CCT)

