15 CHANGES FROM PROTOCOL-STATED ANALYSES

There are no changes to the protocol-stated analyses.

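### SAP Section 15 declares no changes, yet the protocol's MMRM for BCVA and CCT change has become a Month 6 ANCOVA on LOCF values, on which all 14 modelled contrasts rest

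*SAP*

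**What the plan says.** **Protocol.** Section 10.7 analyses change in BCVA and CCT on the full analysis set with "a restricted maximum likelihood based mixed-effect model for repeated measures to evaluate the effect over time". The terms are arm, categorical time, their interaction and baseline. The synopsis gives the same model but miscounts the arms: "The model will include treatment arm (3 levels), categorical time, treatment arm by time interaction, and baseline value as a covariate". The trial has five arms.

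**SAP.** Section 7.8 states: "Change from baseline in BCVA and CCT at Month 6 will be analyzed using Analysis of covariance (ANCOVA) for the full analysis set". Section 7.10 adds that BCVA and CCT "will be imputed using last observation carried forward (LOCF) for their statistical analyses". Section 13.2 repeats both ("As stated in Section 7.10, LOCF will be used to impute the missing values") and promises point estimates, 95% confidence intervals and p-values. For everything else on these endpoints the output is descriptive: "Descriptive summary statistics will be provided for all the secondary endpoints listed in Section 4.2.1.2", and "Change from baseline in BCVA and CCT will also be summarized descriptively using LOCF imputation". No mixed model appears in the readable SAP text. Section 7.9 drops data from the rescue visit onward, so LOCF carries the last pre-rescue value. The completer and per-protocol repeats (13.1.2, 5.2) apply to the primary responder endpoint only.

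**Declared changes.** SAP 15: "There are no changes to the protocol-stated analyses".

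**The concern.** BCVA and CCT change at Month 6 are the first two secondary endpoints, and SAP 7.3 says the study is meant to supply initial estimates for later designs. Someone relying on SAP 15 would not learn that the planned estimator was replaced, or why.

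The two methods treat a lost or rescued eye differently. LOCF lets its last value stand as the Month 6 result and treats it as observed. By the assessment schedule that value could be as early as Week 4 for BCVA or Week 1 for CCT. Under a missing-at-random assumption, MMRM estimates what would have been seen had the eye not been lost. Loss may well differ by arm: Protocol 8.3 offers rescue to eyes that decline, and Protocol 4.5 reports that cells alone did worse than the combination in earlier trials, including on need for rescue.

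At stake is whether the only interval estimates for these endpoints depend materially on one undeclared choice. The other post-baseline visits, also secondary endpoints, lose their modelled estimates altogether.

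**Working it through.** **1. Was the model changed?** Protocol: REML repeated-measures model, all visits. SAP: single-visit ANCOVA on imputed values. These are different analyses, so SAP 15 cannot be right. The SAP cites protocol Version 5.0 and the protocol available is Version 6.0. The log entry for 6.0 lists only one added assessment at one site and gives no sign that the MMRM text was new.

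**2. How many contrasts are affected?** SAP 6.2 compares three combination arms with two components, plus component with component: 3 × 2 + 1 = 7. Two endpoints: 7 × 2 = 14.

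**3. How far might the estimates move?** The plan has no figure to reproduce; every input below is assumed. For each case, 2,000 five-arm trials (20 per arm) were simulated, with arms 1–3 on a better path and arms 4–5 on a worse one. The contrast is arm 1 v arm 5. SD is 12 letters (correlation 0.7) and 70 microns (0.6). Paths (BCVA at Week 4, Months 3, 4.5, 6; CCT also at Week 1):

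- Continuing: 4/10/13/16 v 1/3/4/4; −10/−50/−80/−90/−95 v 20/0/−10/−15/−15
- Plateau: 14/16/16/16 v 4 throughout; −80/−90/−95/−95/−95 v −15 throughout
- Late component recovery (BCVA only): 14/16/16/16 v 0/2/3/4
- Declining component: plateau path v 4/2/0/−2; v −15/−10/0/10/20

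Loss per interval is random at the stated rates, or follows a poor value (20% if the last change was worse than baseline, otherwise 2%). Mean shift of the LOCF contrast from its value with no eye lost (percentage missing at Month 6, arm 1 v arm 5):

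| Case | BCVA, letters | CCT, microns |
|---|---|---|
| Continuing, 5% v 5% | −0.8 (14 v 14) | +4.3 (19 v 19) |
| Continuing, 10% v 10% | −1.6 (28 v 27) | +8.7 (35 v 34) |
| Continuing, 5% v 15% | −0.3 (14 v 39) | +0.1 (19 v 48) |
| Continuing, poor value | −1.0 (18 v 25) | +3.1 (22 v 35) |
| Plateau, poor value | +0.1 (11 v 22) | −1.9 (14 v 31) |
| Late recovery, 5% v 15% | +0.8 (14 v 39) | – |
| Declining, poor value | −0.9 (11 v 25) | +6.2 (14 v 34) |

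True differences are 12 letters (18 if declining) and −80 microns (−115 if declining). Monte Carlo error is about 0.1 letter and 0.5 micron. Within a single trial the LOCF and MMRM estimates differ by a median of 0.6 to 1.6 letters and 5 to 10 microns, with 95th percentiles of 1.9 to 4.3 letters and 17 to 30 microns.

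**4. Do those averages bound the shift?** With random loss *q* per interval, an eye is last seen at visit *k* with probability q(1−q)^(k−1). At *q* = 0.10 the weights are 0.1, 0.09, 0.081 and, for CCT, 0.0729. An arm's shift is the sum of weight × (mean at *k* − mean at Month 6).

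- Check, BCVA, continuing v its own component path: arm 1 = 0.1(−12) + 0.09(−6) + 0.081(−3) = −1.98; arm 5 = 0.1(−3) + 0.09(−1) = −0.39; contrast −1.59. Simulated: −1.6.
- Pair the continuing path with the declining component instead: arm 5 = 0.1(6) + 0.09(4) + 0.081(2) = +1.12; contrast −1.98 − 1.12 = **−3.1 letters**.
- CCT, same pairing: arm 1 = 0.1(85) + 0.09(45) + 0.081(15) + 0.0729(5) = +14.13; arm 5 = 0.1(−35) + 0.09(−30) + 0.081(−20) + 0.0729(−10) = −8.55; contrast **+22.7 microns**.

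A separate two-arm simulation with other assumed paths (5/12/15/17 v 3/0/−3/−5, SD 15, 26% v 44% missing) gave LOCF 18.05 and MMRM 21.83 against a true 22.0, an LOCF shift of −3.95 letters. The averages in the table are therefore not a bound.

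**The case against.** The strongest reply is that SAP 2 lets the SAP supersede the protocol, the study is unpowered and descriptive, and every p-value is nominal. In the simulated cases the mean shifts are small against a root mean squared error of about 4 letters and 23 to 27 microns. LOCF intervals covered the no-loss value in 92% to 96% of trials, and MMRM was slightly less precise in about half the cases. For an eye rescued after decline, carrying the poor pre-rescue value forward answers a defensible question. For BCVA, the 15-letter and 10-letter comparisons count rescue and dropout as failure, and the 15-letter one is repeated in completers and per protocol. The descriptive tables also appear to include observed cases.

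Much of this stands. LOCF-ANCOVA can remain the main analysis, and BCVA has partial cover. It does not answer two things. Precedence settles which method runs, not whether SAP 15 is accurate. And neither CCT change nor BCVA change as a continuous measure has a second contrast with an interval. The observed-case table is only a partial check: where loss followed a poor value, its raw difference also shifted, by −0.5 to −1.2 letters and +3.6 to +8.8 microns.

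A reader might infer more: that LOCF biases the component comparisons in a known direction, or that MMRM has been shown to be right. Neither follows. The sign varied across cases, and the documents supply no inputs to fix it. The simulated losses were all missing at random, so MMRM's near-zero shift was built in and is not evidence for it.

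**Conclusion.** The disclosure error is firm: a planned MMRM was replaced by LOCF-ANCOVA, modelled effects at the other visits were dropped, and SAP 15 says nothing changed. The one inference is that the MMRM text was already in Version 5.0, which was not available; the Version 6.0 log supports this.

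The numerical consequence is uncertain. Under the assumptions shown, mean shifts ran from negligible to about 3 letters and 23 microns (about 4 letters in the separate simulation). Only arm 1 v arm 5 was examined, so nothing is claimed about the size of the effect on the other contrasts. The matter concerns secondary endpoints and does not touch the primary analysis. It should be fixed, but it does not put the trial's main result in doubt.

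**What to change.** 1. **Correct SAP 15.** List the move from MMRM to ANCOVA with LOCF, with its rationale. List also three smaller undeclared changes: the full analysis set (eligible subjects in Protocol 10.5, randomized subjects in SAP 5.1); the per-protocol set (study completers without major deviations in Protocol 10.5; a subset excluding major deviations that affect the primary endpoint in SAP 5.2); and the decision in SAP 14.1 not to tabulate serious TEAEs by severity and relationship, which Protocol 10.8 plans. Overall serious counts, treatment-related serious counts and a listing are kept.
2. **Add the protocol's MMRM as a pre-specified sensitivity analysis** for BCVA and CCT change beside LOCF-ANCOVA, before the Month 6 unmasking if that has not yet happened (the documents do not show). Specify five arms, categorical visit, arm-by-visit and baseline; scheduled visits through Month 6 only, with a stated rule for the optional Month 2 visit; unstructured covariance with a named fallback; small-sample degrees of freedom; and the SAP 6.2 contrasts at Month 6. State which question each analysis answers for a rescued eye.
3. **Minor:** correct the number of arm levels in the synopsis model from three to five.

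The cost is SAP wording and a little programming, with no new data. The downsides are a missing-at-random assumption for rescued eyes and sometimes slightly lower precision than LOCF (for example RMSE 4.1 v 3.8 letters at 14% v 39% missing).

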4.2.1.2 Secondary Efficacy Endpoints

- Change from baseline in BCVA at Month 6
- Change from baseline in central corneal thickness (CCT) at Month 6
- Response, defined as a ≥ 15 -letter improvement (3-line gain) from baseline in BCVA at all other timepoints
- Change from baseline in BCVA at all other timepoints
- Change from baseline in CCT at all other timepoints
- Response, defined as a ≥ 10 -letter improvement (2-line gain) from baseline in BCVA at each timepoint

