7.9 Handling of Data after Rescue

For this study reporting, any data collected at and after rescue visits will not be used for the analyses and summary tables but will be included in the listings. This applies to both efficacy and safety tables as well as concomitant medication tables. The only exception is that adverse events collected at and after rescue visits will be summarized separately as described in Section 14.1.

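### By-visit responder and line-gain tables drop post-rescue data with no stated failure rule or denominator, so their rates may not be comparable with the primary Month 6 rate

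*SAP*

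**What the plan says.** The general rule in SAP 7.9 is that "any data collected at and after rescue visits will not be used for the analyses and summary tables"; such data stay in the listings. SAP 13.2 repeats the rule for the descriptive secondary summaries, which are "provided for all the secondary endpoints listed in Section 4.2.1.2. Any data collected at and after rescue visits will not be used". Two of those endpoints (SAP 4.2.1.2) are responder rates. The 15-letter one is "improvement (3-line gain) from baseline in BCVA at all other timepoints" and the 10-letter one is "improvement (2-line gain) from baseline in BCVA at each timepoint". Section 13.2 adds a table in which "3, 2, and 1-line gain and 3, 2, and 1-line loss in BCVA will be summarized by dose and visit". For that table, "Summaries will include count, percentage and cumulative percentages", and post-rescue data are again excluded. Its categories are gain, loss and 0-line.

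The failure rule is narrower. SAP 7.10 and 13.1.1 count rescue or dropout before Month 6 as failure of the primary endpoint, and 13.1.1 adds a missing Month 6 value. Section 7.10 extends this: "For the statistical analysis, the following two binary endpoints will be imputed using the same method as the primary endpoint". The legible one is 10-letter response at Month 6; the other is blank in the public copy. For the Month 6 10-letter analysis, 13.2 says: "For this analysis, missing data will be imputed using the same method as the primary endpoint". Last observation carried forward (LOCF) is assigned only to BCVA and CCT as continuous measures.

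No passage sets a denominator for the by-visit tables. SAP 6.1 asks for counts and percentages. The FAS denominator in SAP 8 belongs to disposition. SAP 5.1 names the FAS as the main efficacy population. Protocol 10.7 gives only the categories response and non-response.

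**The concern.** Rescue here is keratoplasty in the study eye, so a rescued eye is a treatment failure, and the primary analysis treats it as one. If the same eye disappears from the by-visit tables, the rate at each visit describes only subjects who have not needed rescue. Protocol 8.3 allows rescued subjects to be discontinued after about one month, so many would be absent from later visits anyway.

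Three things are at stake:

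- **Time course.** Durability to Month 12 would be read from these tables, and a shrinking denominator can look like continuing improvement.
- **Comparison of arms.** The design sets the combination against its components. Protocol 4.5 reports that cells alone previously did worse, including on need for rescue, so unequal rescue between arms is foreseeable.
- **Consistency at Month 6.** A 3-line gain at Month 6 is both the primary endpoint and a row of the line-gain table. A 10-letter gain at Month 6 is both an imputed analysis and part of the descriptive summary at each timepoint. Either could be printed with two different rates.

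**Working it through.** The plan states no response rate, rescue rate or power, so there is no figure of its own to reproduce.

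**Step 1: which output carries which rule.** Post-rescue data are unused in all of them.

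| Output | Rescued, withdrawn or missing = failure? | Denominator |
|---|---|---|
| 15 letters, Month 6, primary (SAP 13.1.1) | Yes | All FAS subjects in the arm, by imputation |
| 10 letters, Month 6 analysis (13.2) | Yes | Same |
| Completer analysis, Month 6 (13.1.2) | No, by design | Subjects with observed Month 6 data |
| 15 letters, other visits (13.2) | Not stated | Not stated |
| 10 letters, each visit, descriptive (13.2) | Not stated | Not stated |
| Line gain and loss, each visit including Month 6 (13.2) | Not stated | Not stated |

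**Step 2: the most natural reading of the last three rows.** Three features point to observed cases:

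- The exclusion sentence is the one used for the completer analysis in 13.1.2, which is expressly observed-data.
- Section 13.2 says so where it wants imputation, and it offers LOCF summaries of BCVA and CCT as an addition to the main descriptive ones.
- The line-gain table has no row for rescued or missing subjects.

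**Step 3: size.** Inputs: n = 20 per arm (SAP 4.1). The number of responders seen at the visit, x, and the number of non-responders removed, r, are assumptions.

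- Primary rule: x/n
- Observed cases: x/(n − r)
- Excess: x·r/[n(n − r)], which is zero if x = 0 or r = 0

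| x | r = 0 (primary rule) | r = 2 | r = 4 | r = 6 |
|---|---|---|---|---|
| 3 | 15.0% | 16.7% | 18.8% | 21.4% |
| 6 | 30.0% | 33.3% | 37.5% | 42.9% |
| 12 | 60.0% | 66.7% | 75.0% | 85.7% |

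Withdrawals act the same way: 6 responders, 4 rescued and 2 withdrawn gives 6/14 = 42.9%.

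**Step 4: two rates at Month 6.** With 6 responders and 3 rescued, the primary analysis gives 6/20 = 30.0% and the line-gain table 6/17 = 35.3%. The excess is 6·3/(20·17) = 5.3 points.

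**Step 5: a trend with no eye better.** Take 8 responders at every visit and cumulative rescues of 2, 3, 4, 6 and 8 by Months 3, 4.5, 6, 9 and 12. Observed-case rates are 8/18 = 44.4%, 8/17 = 47.1%, 8/16 = 50.0%, 8/14 = 57.1% and 8/12 = 66.7%. The primary rule gives 8/20 = 40.0% throughout.

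**Step 6: between arms.** Take 12 and 4 responders, with 2 and 10 rescued. The primary rule gives 60.0% − 20.0% = 40.0 points. Observed cases give 12/18 − 4/10 = 66.7% − 40.0% = 26.7 points. The arm with more rescues gains 20.0 points and the other 6.7.

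**The case against.** **The harm is conditional.** A reader might infer that the SAP tells the analyst to remove rescued subjects from the denominator, so that biased rates are certain. The documents do not say that. SAP 5.1 makes the FAS the main efficacy population. With FAS N as denominator and post-rescue data unused, the rate equals x/20 and nothing is inflated. This stands: the defect is an unstated rule whose likeliest reading gives inflated rates. The blank bullet in 7.10 leaves some doubt too, but 7.10 names only two binary endpoints. One further item could not cover both responder series and the line-gain tables.

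**An observed-case table is a legitimate choice, and a Month 6 observed-data rate is already planned.** True, but the completer analysis is declared as such. The by-visit tables are not labelled, and no composite version accompanies them at the other visits.

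**The distortion is not one-sided.** Responders who miss a visit also leave. If 2 of 6 responders are absent, observed cases read 4/18 = 22.2% and the primary rule 4/20 = 20.0%, both below 30.0%. So the observed-case rate is never below the composite rate at the same visit, but neither is free of error. In Step 6 the observed-case basis works against the better arm.

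**The consequence is limited.** The study is unpowered and these tables are descriptive. Counts (SAP 6.1), arm sizes (SAP 8) and rescues by visit with Kaplan-Meier plots (SAP 14.3) are reported, so a careful reader could recompute responders over FAS N. This stands, and it limits the weight of the point without removing it.

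**Conclusion.** The point holds as a gap in the rules for the by-visit tables. Post-rescue data are excluded, the legible failure imputation stops at Month 6, and no denominator is stated. On the observed-case reading, the excess over the primary rule in an arm of 20 runs from 1.7 points (3 responders, 2 rescued) to 25.7 points (12 responders, 6 rescued), and it is zero when nobody is rescued, withdrawn or missing. These figures rest on assumed responder and rescue counts and on only non-responders leaving.

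A reader might also infer that the primary result is inflated. It is not: the primary analysis, its per-protocol repeat and the Month 6 10-letter analysis all use the failure rule, and no planned test is affected. What is at risk is the reading of time trends, durability and dose comparisons from the by-visit tables. The change is worth making before unmasking for the Month 6 report.

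**What to change.** Amend SAP 7.10 and 13.2 as follows.

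1. **Required BCVA visits (Week 4 and Months 3, 4.5, 6, 9, 12).** For the 15- and 10-letter summaries, count subjects rescued at or before the visit, or withdrawn before it, as non-responders. Treat missing values as in the primary rule, and use the arm's FAS N as denominator. Observed-case rates may stand beside these if labelled.
2. **Month 6 report.** SAP 7.1 includes later data in this report, when some subjects will not have reached Month 9 or 12. Show subjects not yet due separately and do not count them as failures. For example, if 10 of 20 have reached Month 9 and 5 respond, 5/20 = 25% would mislead where 5/10 = 50% is meant. Judge who is due by injection date alone, so that rescue does not affect it. Use the full FAS denominator at those visits in the final report.
3. **Optional Month 2 visit.** Label the summary as observed attendees only, show the number already rescued, and do not compare it with the other visits.
4. **Line-gain tables.** Add one row for rescued and one for withdrawn or missing. Make the line categories mutually exclusive: 15 letters for 3 lines and 10 for 2 imply 5 letters per line, so a 1-line change now falls inside the 0-line label for changes under 10 letters. The Month 6 3-line-gain percentage should then equal the primary rate.
5. **Completer analysis.** Keep it, labelled as observed data without rescue.

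The cost is SAP wording and minor programming, with no new data. By-visit rates will look somewhat less favourable. In the composite version a single missed visit counts as non-response, so 6 responders of whom 2 miss a visit read 4/20 = 20.0% instead of 30.0% with no eye worse. This is a reason to show observed-case rates alongside.

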4.2.1.1 Primary Efficacy Endpoints

- Response, defined as a ≥ 15 -letter improvement (3-line gain) from baseline in best-corrected visual acuity (BCVA) at Month 6

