7 STATISTICAL METHODS

7.1 Study Reporting

There will be two reporting events for this study, one reporting when all subjects complete Month 6 visit and another reporting when all subjects complete the study (Month 12 visit). For the first reporting, when all subjects complete the Month 6 visit, data will be cleaned and frozen at the subject visit level. The sponsor will be unmasked for the 6 months efficacy and safety analyses. AE starting after the Month 6 visit will not be included for Month 6 reporting for better risk-benefit assessment. All other data after Month 6 visit will be included and reported as they are. For the second data reporting, when all subjects complete the entire 12-month study, data will be cleaned, and the database will be locked.

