14.2 Vision Loss

The number and percentage of subjects who have loss from baseline in BCVA ≥ 15 letters will be summarized using counts and percentages at each post-baseline visit by treatment group and overall.

The best corrected visual acuity will be presented in a listing.

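### The 0-line row of the BCVA line-change table takes in every change under 10 letters, so it overlaps the 1-line gain and 1-line loss rows of the same table

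*SAP*

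**What the plan says.** SAP 13.2 plans a categorical table of BCVA change: "3, 2, and 1-line gain and 3, 2, and 1-line loss in BCVA will be summarized by dose and visit". The next sentence adds a further row to it: "Change from baseline within 10 letters (<10 letters gain and <10 letters loss) will be labeled as 0-line". The statistics are then specified: "Summaries will include count, percentage and cumulative percentages".

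The only links between lines and letters are in the endpoint definitions. SAP 4.2.1.1 sets the primary response at 15 or more letters, a "letter improvement (3-line gain) from baseline in best-corrected visual acuity (BCVA) at Month 6". SAP 4.2.1.2 sets the lower threshold at 10 or more letters, a "letter improvement (2-line gain) from baseline in BCVA at each timepoint". Neither document gives a letter range for a 1-line gain or loss. The protocol does not describe this table, so SAP 13.2 is its only specification.

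**The concern.** With 3 lines at 15 letters and 2 lines at 10, the implied scale is 5 letters per line. A 1-line change below the 2-line threshold is then 5 to 9 letters, and the 0-line definition already claims all of those values. No rule says which row wins.

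A programmer has three ways to proceed, and each produces a different table:

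- **0-line takes precedence.** The 1-line rows are always empty, and gains and losses of 5 to 9 letters are reported as no change.
- **Both rows count.** Subjects appear twice and the percentages can exceed 100%, which makes the cumulative percentages meaningless.
- **0-line is narrowed.** The rows work, but the output contradicts the SAP's written definition.

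The table is presented by dose and visit in a dose-ranging study. The only other categorical summary of vision loss, in SAP 14.2, starts at 15 letters, so this table is the only place where smaller losses would be categorised.

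**Working it through.** **Inputs.** From the SAP: 3-line gain is 15 or more letters (4.2.1.1), 2-line gain is 10 or more (4.2.1.2), 0-line is any change from −9 to +9 (13.2), and there are about 20 subjects per arm (4.1). Inferred: 5 letters per line, from 15/3 = 10/2 = 5, with the cut-offs mirrored for losses. The plan gives no figure of its own to reproduce here.

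**Step 1: assign each whole-letter change from −60 to +60 to rows.**

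| Change (letters) | Line row | Also 0-line as written? |
|---|---|---|
| 15 or more, either direction | 3-line | no |
| 10 to 14, either direction | 2-line | no |
| 5 to 9, either direction | 1-line | **yes** |
| −4 to +4 | none | yes |

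Ten values (+5 to +9 and −9 to −5) fall in two rows. No value is left without a row.

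**Step 2: does this depend on the inferred 5 letters?** It does not. The 2-line row starts at 10, so any exclusive 1-line row beneath it lies wholly inside the under-10 band. If 1-line is instead read cumulatively as 5 or more letters, changes of 5 to 9 still meet both definitions.

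**Step 3: arithmetic of double counting.** If k of 20 subjects are in the 5–9 band and both rows count, the rows total 20 + k. For k = 2, 4 and 6 the totals are 22, 24 and 26, or 110%, 120% and 130%.

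**Step 4: how many eyes could be in the band.** The documents give no distribution of change, so the following is assumed: normal change with mean m in {0, 5, 10, 12, 15, 20, 25} letters, SD s in {10, 12, 15}, and a continuity correction for whole letters:

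P(a..b) = Φ((b + 0.5 − m)/s) − Φ((a − 0.5 − m)/s)

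The disputed band is P(5..9) + P(−9..−5).

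- For m = 0, s = 10: P(5..9) = Φ(0.95) − Φ(0.45) = 0.155, and P(−9..−5) is the same by symmetry. The total is 0.311, or 6.2 of 20.
- For m = 25, s = 10: P(5..9) = Φ(−1.55) − Φ(−2.05) = 0.040 and P(−9..−5) = Φ(−2.95) − Φ(−3.45) = 0.001. The total is 0.042, or 0.8 of 20.

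The share is the disputed band divided by P(−9..9):

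| Mean / SD | Disputed band | Of 20 | P(−9..9) | Share of written 0-line |
|---|---|---|---|---|
| 0 / 10 | 31.1% | 6.2 | 65.8% | 47% |
| 5 / 12 | 26.4% | 5.3 | 53.3% | 49% |
| 15 / 12 | 16.4% | 3.3 | 30.3% | 54% |
| 20 / 15 | 11.8% | 2.4 | 21.7% | 54% |
| 25 / 12 | 5.9% | 1.2 | 9.6% | 62% |
| 25 / 10 | 4.2% | 0.8 | 6.0% | 69% |

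Across all 21 combinations the band runs from 4.2% to 31.1%, and its loss part from 0.1% to 15.5%. Counts would be lower in practice, because SAP 13.2 excludes data at and after rescue.

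**The case against.** The strongest reply is that little depends on this table. It is an addition to the listed secondary endpoints and carries no test, interval or p-value, and the SAP calls its analyses descriptive. Little information is lost either: change from baseline in BCVA is summarised as a continuous variable, and again with missing values filled in ("Change from baseline in BCVA and CCT will also be summarized descriptively using LOCF imputation"). The 10- and 15-letter gains are summarised by timepoint, the 15-letter loss by visit, and BCVA is listed by subject, so changes of 5 to 9 letters can be recovered. Empty 1-line rows or percentages above 100% would probably be noticed when output is first reviewed. All of this stands, and it limits the effect to one table.

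The assumed percentages also need care. They count eyes in a band and do not show that any conclusion moves. The 31% comes from an arm with no average gain. The 69% share comes from a case where only about 6% of eyes, roughly 1 of 20, are in the 0-line band at all.

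The unstated direction of cumulation is a table-layout matter and would not justify a comment alone.

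None of this removes the contradiction. Noticing it at first output means resolving it then, possibly with treatment assignments known. Nothing in either document settles it, and no redaction or gap in the text accounts for it.

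**Conclusion.** The concern holds. The two consecutive sentences of SAP 13.2 cannot both be carried out as written: with 2-line starting at 10 letters, no exclusive 1-line row can exist outside the 0-line row. That conclusion needs only the SAP's own thresholds.

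The size rests on the assumed normal distributions: 4% to 31% of eyes, about 1 to 6 of 20 per arm, towards the low end where the mean gain is large. The consequence is confined to this supplementary descriptive table. It should be corrected, but it does not threaten the primary or the tested secondary analyses, or the safety summary of 15-letter loss.

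**What to change.** State in SAP 13.2 the letter range of every row, so that the rows are mutually exclusive, and say in which direction percentages are cumulated. Either of these removes the overlap:

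- **Narrow 0-line:** 3-line 15 or more letters, 2-line 10 to 14, 1-line 5 to 9, 0-line −4 to +4, mirrored for losses. Every change from −60 to +60 then falls in exactly one row. The cost is replacing the only 0-line cut-off the SAP states.
- **Keep 0-line at under 10 letters** and delete the two 1-line rows. The cost is losing the 1-line detail.

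The documents do not show which was intended, so the choice is the sponsor's. It should be recorded before the Month 6 reporting, since SAP 7.1 says "The sponsor will be unmasked for the 6 months efficacy and safety analyses" and the categories should not be settled with results by arm in view. The change is one sentence, and no other analysis is affected.
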